The Virtual Reality Insertion of Chest-drain Outcomes Research (VICTOR) study will compare the traditional teaching of chest drain insertion against an immersive Virtual Reality (VR) training system. Junior and senior anaesthetic registrars will be the targeted study population and will be randomly assigned to one of the two study groups. The traditional education group will receive instruction on chest drain insertion via written text and an instructional video. The VR education group will receive instruction via the VR software training programme. After instruction, both groups will be assessed by two blinded researchers using a validated chest drain insertion assessment tool.

Assessment of chest drain insertion will be done by utilizing a simulation mannikin fitted with a chest drain insertion module. Any differences between the traditional training group and the VR group will be assessed by measuring the following outcomes; Scores recorded on a validated checklist for chest drain insertion proficiently, time to completion of the task and the number of deviations from the checklist. Self-reported participant confidence will also be recorded.

2 Rationale / Background

Virtual reality is a computer-generated 3D virtual environment. This virtual environment can be defined as one that "capitalizes upon natural aspects of human perception by extending visual information in three spatial dimensions", "may supplement this information with other stimuli and temporal changes" and "enables the user to interact with the displayed data (1)." The ability to create virtual worlds that the user can then interact with makes VR a potentially useful simulation-based education tool.

Due to the multitude of terms used to describe virtual reality education (VRE) the following table has been included. The included table (2) provides specific definitions for terms related to VRE.

Table 1: Standard definition of terms

Г

Virtual Simulation A screen-based simulation where the graphics, sound
--

	emphasize the 3D nature of the environment.	
Virtual Reality	Use of immersive, highly visual, 3D characteristics to replicate real-life situations; typically incorporates physical or other interfaces such as a head-mounted display, motion sensors, or haptic devices in addition to computer keyboard, mouse, speech, and voice recognition. The user interacts as if it takes place in the real world and the focus of the interaction remains in the digital environment.	

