There are a number of advantages in the use of VRE and these include; repeatability, portability, selfdirected learning, data collection, and cost (8). Taekman et al attribute further human elements such as, instant feedback, rewards, competition, scalability, standardisation and convenience (9).

Virtual Reality Education provides an opportunity to deliberately practise rare, potentially lifesaving procedures and scenarios in a risk-free environment. These advantages make VRE an attractive educational tool, provided that the virtual reality education program is at least as effective or superior to the traditional education method. This remains the motivation behind this pilot study.

3 **Project Aims / Objectives / Hypotheses**

Primary objectives: Compare the effectiveness of VRE training with traditional education methods for the placement of a chest drain by anaesthesia registrars. Effectiveness of education will be assessed by proficiency of chest drain insertion, non-deviation from standardised chest drain checklist and the time taken to complete the task of chest drain insertion.

Secondary Objectives: Assessment of registrar levels of confidence regarding chest drain insertion pre- and post-educational sessions.

Hypothesis: VRE training is as effective if not superior to a traditional teaching approach for the insertion of chest drains.

Null Hypothesis: There is no difference in chest drain insertions outcomes when instructed by either a traditional or VR training approach.

4 Project Design

Project Design

Pilot study

Pre-test survey assessing prior chest drain insertion training; number of chest drain insertions performed in patients; current confidence level related to chest drain insertion ability.

Subjects randomly assigned to one of two groups

Traditional teaching method. Text and instructional video Virtual reality training method

All study participants will be assessed by two anaesthetic consultants blinded to group allocation using a validated checklist for chest drain competency. Chest drain insertion success with be assessed using scores from assessment tool, number of deviations from the checklist, time to task completion and self-reported chest drain insertion confidence levels.

Source and Selection of Participants

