Once all participants have completed their allocated training program and have been subsequently assessed by a blinded assessor the data collection process will end.

5 Treatment of Participants

Description and justification for treatments, interventions or methods to be utilised

The hypothesis that the VRE may prove to be a more effective training method is of potential benefit to all the study participants and patients, especially as this technology becomes more widely incorporated into medical training. The *"Traditionally trained"* group will not be disadvantaged as this is currently the accepted standard of training. Furthermore, access to the VR training software will be made freely available to all participants once their blinded assessment has been completed.

Permitted medications/treatments

There is no medication or treatment in this study.

Monitoring of participant compliance

Onsite facilitators will be present to conduct the virtual reality training session. Facilitators will further ensure that the traditional group reads the notes provided and watches the instructional video.

6 Assessment of Efficacy

Outcomes

Raw scores on the validated chest drain insertion competency checklist

Any deviation from the validated checklist

Time taken for task completion

Matched confidence scores using Likert data from a pre- and post-intervention survey.

Efficacy assessment

The TACTIC validated checklist for chest drain insertion competency will be used (10). The assessors will determine the number of deviations from the checklist and record the time taken to complete the procedure. Confidence levels will be assessed via matched Likert data.

7 Assessment of Safety

Risks and Benefits

Potential risks to the participants include motion sickness, nausea and headaches from the virtual reality training programme. Facilitators will attempt to improve comfort and ensure correct use of the virtual reality headsets in order to limit these effects. Infection risk and cross contamination will be managed by the use of a UVC irradiation device.

Emergent chest drain insertion is a potentially life-saving procedure and the benefits for potentially improving knowledge and skill of chest drain insertion is enormous.

Safety

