Facilitators will be present and monitor for any ill effects developing as a result of the training intervention. Infection control will be provided via UVC irradiation device, used on the virtual reality headset. The controllers will be wiped down with disinfectant wipes between uses.

Adverse events reporting

Any adverse events will be reported via the research team.

- Minor event: follow up with candidate
- More serious event: Regular follow up until resolved/ referral to care provider as determined by independent assessment.

Follow-up of Adverse Events

Any adverse events will be followed up until resolution of any symptoms.

8 Data Management, Statistical Analysis and Record Keeping

Statistics and Interim Analysis

Wilcoxon signed-rank test will be employed to assess any differences that may exist between the two groups. Likert-type questions will be used to obtain self-reported confidence data pre- and post-educational sessions. The median results of the Likert-type questions will be shown to describe central tendency.

Sample Size

The pilot project will use a convenience sample of Anaesthesia registrars at FSFHG. Currently there are 51 registrars. All registrars will be approached to participate. The study is a proof of concept study. Due to the fact that virtual reality software has only recently been developed, there is to the best of our knowledge no other published data to refer to. If a difference is noted between the study groups, a power analysis will be conducted to calculate the sample size necessary in a follow up study, to confirm differences that may exist.

Study Power and Significance

A validated checklist will be used to assess each candidate's placement of a chest drain. This checklist has 20 steps, graded out of 40 points, that must be completed in order for the chest drain placement to be deemed safe & successful. The mean score of the two study groups will be compared. A difference in the mean score p value of 0,05 will be deemed significant.

A power analysis will be conducted for a subsequent study, based on the results of this pilot trial.

As there is no data for VR teaching in terms of medical procedures in anaesthesia this study will provide a baseline comparison to traditional teaching. Certainly, an increase of 20% in the mean score would be seen as significant.

Statistical plan deviations

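### Confidence is listed among the outcomes for judging the two teaching methods, but no analysis stated for it gives a valid comparison between the arms

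*Protocol*

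**What the plan says.** The protocol describes the role of confidence in two ways.

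- **As an outcome for judging the methods.** Section 4, Project Design, sets out the two randomised groups and then lists what insertion success will be judged on: checklist scores, "number of deviations from the checklist, time to task completion and self-reported chest drain insertion confidence levels". Section 6, Outcomes, gives it as the fourth efficacy outcome: "Matched confidence scores using Likert data from a pre- and post-intervention survey".
- **As a pre/post measure only.** The opening summary names checklist score, time and deviations as the outcomes for differences between the groups, then adds "Self-reported participant confidence will also be recorded". The secondary objective in Section 3 is "Assessment of registrar levels of confidence regarding chest drain insertion pre- and post-educational sessions", with no contrast between arms.

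Three statements bear on its analysis.

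- Section 6, Efficacy assessment: "Confidence levels will be assessed via matched Likert data".
- Section 8, Statistics and Interim Analysis: "Wilcoxon signed-rank test will be employed to assess any differences that may exist between the two groups". This is not limited to any outcome.
- The same paragraph, after saying that confidence is collected before and after the session: "The median results of the Likert-type questions will be shown to describe central tendency".

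**The concern.** Both arms are taught, so confidence can be expected to rise in both. A rise within the VR arm therefore says nothing about VR against text and video; only a contrast between the randomised arms does. The methods written down are within-person (matched data), descriptive (medians), or a paired test assigned to two unpaired groups.

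At stake is how the confidence result is read. Section 13 intends publication, and Section 8 intends the pilot's results to inform a follow-up study. Anyone applying the signed-rank test where it is valid, to matched pre/post scores, would obtain one p-value per arm. It would then be easy to take a significant rise in one arm and a non-significant rise in the other as evidence about VR, which it is not.

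**Working it through.** The protocol gives no power, effect size or sample-size calculation for confidence, so there is no figure to reproduce. The check is first by logic, then by illustration.

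**Each stated method against the question: did VR raise confidence more?**

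- *Matched Likert data.* Matching is between one person's pre and post scores. It estimates change within a person and, averaged, within an arm. No arm contrast is stated.
- *Medians.* Equal medians can hide unequal gains. Take a constructed example with 25 per arm and identical pre scores (eight 1s, nine 2s, eight 3s). In arm A everyone gains 1. In arm B the 1s go to 3, the 2s to 3 and the 3s to 5. Both arms have pre median 2 and post median 3. Mean gain is 1.00 in A and (8×2 + 9×1 + 8×2)/25 = 41/25 = 1.64 in B. A Mann-Whitney test on the changes gives p < 0.00001.
- *Signed-rank test.* It needs pairs. Section 4 assigns participants at random to separate groups, so there is no pairing across arms. For confidence its valid use is pre against post, which is again within-arm.

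**How far within-arm tests can mislead (illustration).** With identical arms and within-arm power p, exactly one arm is significant with probability 2p(1−p):

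- p = 0.5: 2×0.5×0.5 = 50%
- p = 0.8: 2×0.8×0.2 = 32%
- p = 0.9: 2×0.9×0.1 = 18%

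A simulation agrees. It used 2,000 runs, 25 against 26 participants, a 1–5 scale, baseline SD 0.8, change SD 1.0 and alpha 0.05, all assumed except that 25 + 26 = 51, the head count in Section 8.

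- Equal true gains of 0.5: exactly one arm was significant in 45% of runs. A Mann-Whitney test between arms on change rejected in about 5%, as it should.
- True gains of 1.0 and 1.5: both arms were significant in 99.6% of runs, so within-arm tests do not separate arms that truly differ.

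**What baseline adjustment gains.** For pre/post correlation r and equal variances, the variance of the adjusted arm effect is (1−r²)/(2(1−r)) = (1+r)/2 of that for change scores, and 1−r² of that for post scores alone:

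| r (assumed) | against change | against post only |
|---|---|---|
| 0.3 | 0.65 | 0.91 |
| 0.5 | 0.75 | 0.75 |
| 0.7 | 0.85 | 0.51 |

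**What an arm comparison could detect.** With 25 and 26 participants, √(1/25 + 1/26) = 0.280. At two-sided alpha 0.05 (assumed):

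- 0.5 SD, unadjusted: Φ(0.5/0.280 − 1.96), about 43%
- 0.8 SD, unadjusted: Φ(0.8/0.280 − 1.96), about 81%
- 0.5 SD, adjusted at r = 0.5: 0.5/√0.75 = 0.577, then Φ(0.577/0.280 − 1.96), about 54%

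**The case against.** The strongest reply has four parts.

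1. *A between-group test is stated.* The Wilcoxon sentence is not limited to any outcome and stands in the same paragraph as the confidence sentences. A reader might infer that the protocol plans nothing for confidence beyond medians; the text does not support that. What remains is that the named test is the wrong kind for independent arms. If the name is a slip for the rank-sum test, the repair is small, but the protocol says signed-rank, and matched data in Section 6 point the same way.
2. *Confidence may never have been meant as an arm comparison.* The summary and the secondary objective support this, and matched data with medians suit a pre/post objective. A reader might infer that the secondary objective fails at its task; it does not, since as worded it claims no arm contrast. But Sections 4 and 6 place confidence among the outcomes for judging the methods, so its role is unsettled.
3. *Model detail belongs in a SAP, which may exist.* That is right: silence on covariates is not a fault in itself. The point rests on what the protocol does fix (a test, a data structure and a summary), which together do not answer the comparative question.
4. *No one proposes to contrast within-arm p-values.* This stands in full. A reader might infer that such a contrast is planned; nothing in the protocol says so. The 32% and 45% figures show the risk of a misreading, not an error in the stated plan.

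A reader might also want to know how often the two medians would coincide despite a real difference. That depends on the number of response categories and where scores fall among them. The survey in Appendix 1 is not shown, so no rate is given here.

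**Conclusion.** The point holds in a limited form. The protocol is inconsistent about whether confidence is a within-person or a between-arm outcome. Followed as written, its methods yield no valid VR-versus-traditional contrast for confidence. This follows from the text and needs no assumption.

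The sizes do rest on assumptions. The 32% needs identical arms and 80% within-arm power (18% to 50% over powers of 90% to 50%). The 25% saving in variance needs a pre/post correlation of 0.5; over 0.3 to 0.7 the saving is 35% to 15% against change scores and 9% to 49% against post scores alone. Medians are a sound description and need not be removed. Since this is a secondary self-report outcome in a pilot with at most 51 participants, even a correct comparison would be imprecise. The change is worth making because it is nearly free, not because the trial's main result depends on it.

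**What to change.** In Section 8, and consistently in the summary and Sections 3, 4 and 6:

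- State whether confidence is a within-person outcome, a between-arm outcome, or both.
- Keep medians, and the signed-rank test if it is used, to describe pre/post change within each arm. State that within-arm p-values are not evidence about VR.
- For the arm comparison, analyse post-session confidence with a proportional-odds or linear model containing arm, pre-session confidence and the junior/senior stratum already used in the randomisation. Mann-Whitney on the change scores is a simpler alternative, though it leaves out the stratum and uses the pre score only by subtraction.
- Report the arm effect with a 95% CI and label it exploratory.

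The cost is a few sentences and a little analysis. Pre- and post-session confidence and the seniority stratum are already in the planned data, so nothing new is collected.

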The study participants will be the junior and senior anaesthetic registrars from the Fiona Stanley & Fremantle Hospital Group Department of Anaesthesia & Pain Medicine. An email will be sent by [name] containing information regarding the study and a request for participation.

Participant inclusion criteria.

All the registrars in the Fiona Stanley & Fremantle Hospital Group Department of Anaesthesia & Pain Medicine as of 3rd August 2020.

Participant exclusion criteria.

Unwilling to participate or sign consent.

Not completing the chest drain training.

Adverse reaction to virtual reality hardware.

Previous use of the VR chest drain scenario if allocated to the control group.

Participant withdrawal criteria

If unable to use the virtual reality training program due to motion sickness, nausea or headache. The facilitators will attempt to improve the comfort of the headset. If the participant still cannot use the headset due to discomfort they will be removed from the study.

Bias

The participants will be allocated to groups by computer-generated randomisation. The assessors of the two groups will be blinded to the training method that all the participants received.

Blinding and Randomisation

Due to the varying skills/capabilities of the junior and senior registrars, the two groups will be randomised separately to ensure an equal balance between the control and experiment groups.

The researchers will have a separate list of participants that will contain the information regarding which training method each participant received. This will be correlated against the score sheets from the blinded assessors.

Method

The traditional education group will use the teaching material from the Emergency Trauma Management (ETM) course manual. This course is accredited as part of the professional development program by the Australian College of Rural and Remote Medicine. The VR education group will use the novel VR training software. Assessment of the two groups will be performed on a SimMan 3g mannikin with a chest drain module inserted. The assessment tool used is a validated checklist for chest drain insertion proficiency.

Project Duration/Schedule

The expected duration of data collection is six months. Data analysis is expected to take a further 6 months to complete. This includes the writing of a research manuscript for publication.

Project Termination

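### Section 8 decides the checklist score on a difference in means, but the only between-group test it names is a paired rank test, which neither fits independent arms nor tests means

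*Protocol*

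**What the plan says.** Three statements in Protocol section 8 bear on the checklist score.

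- **The test** (Statistics and Interim Analysis): "Wilcoxon signed-rank test will be employed to assess any differences that may exist between the two groups". No other between-group test is named in the protocol.
- **The decision rule** (Study Power and Significance): "The mean score of the two study groups will be compared. A difference in the mean score p value of 0,05 will be deemed significant".
- **The benchmark** (same subsection): "Certainly, an increase of 20% in the mean score would be seen as significant". Whether 20% is relative or absolute is not said.

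The score is bounded: "This checklist has 20 steps, graded out of 40 points". On numbers, the Sample Size subsection says: "Currently there are 51 registrars. All registrars will be approached to participate". On allocation, section 4 (Blinding and Randomisation) says of juniors and seniors that "the two groups will be randomised separately to ensure an equal balance between the control and experiment groups". The only matched data listed in section 6 are the confidence scores before and after training. Medians are mentioned only for describing the Likert items.

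**The concern.** The decision rule and the benchmark are both on the mean, while the named test works on ranks of paired differences. There are two faults in one sentence.

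1. **Pairing.** The signed-rank test needs each VR score to be matched to one traditional score. Registrars are randomised to separate arms, and nothing pairs them.
2. **Target.** Even after the obvious repair to the unpaired rank-sum test, the p value does not belong to a difference in means. The rank-sum test asks whether scores in one arm tend to exceed those in the other. The two questions coincide if the arms differ only by a shift. The protocol does not assume that, and a pure shift is hard to sustain on a score capped at 40.

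At stake is what a reported p value would mean. A rank p value presented under the mean-score rule could reflect a difference in spread or shape. With no rule for which analysis decides, the choice could also be made after the data are seen. Section 8 makes the power analysis for a follow-up study depend on noticing a difference here.

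**Working it through.** The protocol gives no power, SD or expected mean, so it has no figure to reproduce. The check has three parts.

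**1. Can the named test be run?** If all 51 take part in near-equal arms, the split is 26 v 25. Signed-rank needs equal numbers in pairs, so it cannot be computed. With equal arms the result depends on an arbitrary pairing. In one simulated 25 v 25 data set, 2,000 random pairings gave signed-rank p values from 0.007 to 0.37, with 12.8% below 0.05. On the same data the rank-sum p was 0.063 and the t-test p was 0.082.

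**2. Do means and ranks answer the same question?** A constructed example on the 0-40 scale:

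- Group 1 (n = 25): five scores each of 28, 29, 30, 31 and 32. Mean 30.0, median 30.
- Group 2 (n = 26): six of 12, six of 32, seven of 33, seven of 34. Mean (72 + 192 + 231 + 238)/26 = 733/26 = 28.2, median 33.
- Means: difference 30.0 − 28.2 = 1.8 in favour of group 1, Welch t = 1.00, p = 0.33.
- Ranks: U for group 1 = 25 × 6 (wins over the scores of 12) + ½ × 5 × 6 (ties at 32) = 165 of a possible 25 × 26 = 650. That is 25%, in favour of group 2, with p = 0.002.

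One test is significant and the other is not, and the estimates point in opposite directions.

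**3. How often would it matter?** Welch t-test v rank-sum test, 26 v 25, two-sided 0.05. Scores are beta-binomial out of 40 with mean proportion m and concentration c, so that SD = √[40·m(1−m)·(c+40)/(c+1)]. For m = 0.80:

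- c = 20: √(6.4 × 60/21) = 4.3
- c = 4: √(6.4 × 44/5) = 7.5
- variance ratio: 56.3/18.3, about 3

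All means and concentrations are assumptions. The runs used 4,000 or 5,000 trials per scenario.

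| Mean (% of maximum) | Concentration | Welch rejects | Rank-sum rejects | Tests disagree |
|---|---|---|---|---|
| 75 v 75 | 8 v 8 | 5.2% | 5.0% | 2.5% |
| 80 v 80 | 12 v 8 | – | 4.8% | 2.3% |
| 80 v 80 | 20 v 10 | – | 6.0% | 3.3% |
| 60 v 60 | 20 v 4 | – | 6.2% | 3.2% |
| 75 v 82 | 8 v 8 | 36.8% | 37.4% | 8.5% |
| 75 v 90 (relative +20%) | 8 v 8 | – | – | 1.6% |
| 80 v 80 | 20 v 4 | 5.7% | 14.5% | 10.8% |
| 85 v 85 | 20 v 4 | 6.2% | 18.4% | 14.7% |

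(A dash means the figure is not reported here.)

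A second model (rounded normal scores clipped to 0-40, 25 v 26, 10,000 runs) gives the same picture:

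- no effect, SD 6: 1.9% disagreement
- 28 v 32, SD 6: 5.6%
- 28 v 33.6 (+20%), SD 8: 5.5%
- near-equal means with a low-scoring tail in one arm: 15.1% (rank-sum rejects 17.8%, Welch 5.3%)

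In no run of this second model were both tests significant in opposite directions.

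**The case against.** Several points against the concern have force.

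- **The large figures need an extreme case.** Concentration 20 v 4 means a variance ratio of about 3, with 12% of the wider arm scoring a perfect 40 at mean 80% and 21% at mean 85%. Nothing in the protocol points to such scores. With milder inequality, or with means of 60%, the effect nearly vanishes. This stands, and it limits the size.
- **At the protocol's own benchmark the choice seldom matters.** A 20% relative rise gave 1.6% disagreement in one model and 5.5% in the other. This stands too.
- **The study is a pilot on a convenience sample.** A noted difference leads to planning a further study rather than to a change in practice. This lowers the stakes but does not make the two sentences agree.
- **A rank contrast would be a legitimate choice for a bounded checklist.** True. But keeping it would mean rewriting the decision rule and the benchmark, both of which are now on the mean.
- **An analysis plan that is not shown could settle it.** It could choose, but only by departing from one of two protocol sentences. The conflict is stated, not merely left open.

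A reader might infer more than the documents support:

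- That the two tests would give opposite verdicts on the same 51 registrars. The disagreement is between significant and not significant, and 51 is the pool approached. Non-consent, withdrawal and the exclusion of incomplete checklists can all reduce the number analysed.
- That two tests give two chances to cross 0.05. The protocol does not propose running both, and with identical arms either one is significant in only 6.4% of trials.
- That the 20% remark is a claim to be proved by the rank test. The protocol links it to no test or interval.

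**Conclusion.** The contradiction is real and lies within section 8. The p value is attached to a difference in mean score, while the only named between-group test is paired and rank-based. It cannot properly be applied to these independent arms, and it would not yield the stated p value if it could. Correcting the pairing alone leaves the mismatch in place, so both faults belong in one correction.

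The numerical consequence is modest in ordinary conditions: about 2% to 8.5% disagreement on significance with similar or mildly unequal spread. It rises to about 11% to 15%, with rank-sum rejection of 14% to 18% at equal means, only when one arm is much more spread out near the ceiling or has a low-scoring tail. These figures rest on assumed distributions and on all 51 taking part. The textual fault does not depend on them. It should be corrected before analysis, but it is no ground for expecting the trial's result to be wrong.

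**What to change.** In section 8, replace the signed-rank test for the checklist score with one analysis that matches the stated rule:

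- Estimate the difference in mean checklist score, VR minus traditional, with a 95% confidence interval and a two-sided p value from a Welch-type or heteroscedasticity-robust comparison of independent groups. Account for the junior/senior randomisation groups. State that this result decides at 0.05.
- Read the 20% benchmark against the same interval, and say whether 20% is relative to the traditional-arm mean or a share of the 40 points (20% of 40 = 8 points).
- If a rank-sum test is wanted, label it a sensitivity analysis that cannot replace the mean result.
- Keep the signed-rank test only for the matched pre- and post-training confidence scores.

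The cost is one or two sentences of wording and no new data. The small downside is that a mean comparison is somewhat more sensitive to an outlying score, which the rank sensitivity analysis would reveal.
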